
2. Objectives (include all primary and secondary objectives)

The specific aims of this proposal are as follows:

- (1) To measure the effect of a peer mentoring program on mild to moderate depression compared to social interaction control among minority and low-income adults aged 50+ years recruited from primary care clinics;
H1: Older adults randomized to the Peer Program (vs. control) will report decreased depression (PHQ-9 score decrease ≥ 5) at 8 weeks, 3, 6, 9 and 12 months.

We will conduct a randomized controlled trial by enrolling 160 low-income and minority adults and measure the effect of the Peer Enhanced Depression Care Program on mild to moderate depressive symptoms compared to Social Interaction Control. We will recruit a total of 10 peer mentors. The supervised peer mentors who are based in the community will provide social support by telephone with depressed older adults recruited from primary care and the

community for 8 weeks with initial training and ongoing supervision by a clinical social worker. The core components of the Peer Program are: (1) relationship building, active listening, emotionally responsive and patient-centered communication, (2) sharing of experiential knowledge by peer mentors, sharing of coping skills, modeling and communication of positive health messages regarding self-care (3) linkage to community and clinical mental health resources. In Aim 2, we will conduct a quantitative mediation analysis, specifically measuring increase in self-efficacy as the mediating factor. In Aim 3, we will use post-study key informant interviews from a diverse group of stakeholders representing individuals, the community and the primary care clinic to assess implementation process, and we will use checklists to evaluate the fidelity of the intervention.

3. Background (briefly describe pre-clinical and clinical data, current experience with procedures, drug or device, and any other relevant information to justify the research)

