- If eligible, conduct clinical evaluation by telephone to assess eligibility for the study
- If not eligible, participant will be given information and a list of community and clinical resources
- If eligible, patient will undergo a baseline assessment
- Participant will be asked if willing to take part in 8 peer meetings, and 6 assessments, or Social interaction/health education visits and assessments by phone.
- If yes, we will proceed to obtain oral consent and enrollment.
- Randomization occurs
- If intervention condition -- contacted by Peer mentor -- begin 8 meetings by phone
- If control condition -- contacted by Study staff and social interaction visits
- Data collected and flagged for urgent referral if needed
- Intervention and Control conditions contacted by Study coordinator to conduct interviews by telephone, post-intervention after 8 visits and at 3 months, 6 months, 9 months and 12 months

We will collaborate with Baltimore CONNECT that was formed as a research partnership in 2013 between Johns Hopkins University and 20+ community-based social organizations. They provide a range of services from peer counseling to workforce development and nutrition support, and is now a designated non-profit. We are guided by community-engaged principles of research emphasizing a partnership approach that is equitable and includes diverse research partners.(32) The Advisory Board of Baltimore Connect will assist with recruitment of peers and help connect older adults to social services they offer. The Advisory Board will give input regarding issues of ethnicity and community culture. Preliminary findings of quantitative and qualitative analyses will be presented at quarterly meetings of the Advisory Board for feedback and interpretation, and will be integrated into the final results.

Study participants

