Inclusion/exclusion criteria for peers: Inclusion criteria: (1) 50 years and older, (2) history of depression, (3) at least 5 years in recovery, and (4) received basic training in behavioral health or have volunteer experience in mental health. Exclusion criteria: (1) meet current diagnostic criteria for Major Depressive Disorder; (2) meet current diagnostic criteria for a manic episode or a psychotic disorder; (3) meet current diagnostic criteria for substance abuse disorder.

Inclusion/exclusion criteria for depressed older adults: Inclusion criteria are: (1) 50 years and older; (2) depressive symptoms with PHQ-9 scores ≥ 5 ; (3) belong to an underserved population, defined as annual income less than 200% of the federal poverty level (\$24,120) or self-identified ethnic minority; (5) able to communicate in English; and (6) willing to give informed consent. Exclusion criteria are: (1) meet diagnostic criteria for mania or hypomania; (2) meet diagnostic criteria for psychotic syndrome; (3) meet diagnostic criteria for substance abuse or dependence; (4) acutely suicidal; and, (6) a score on the Mini-Mental State Examination (MMSE) ≤ 24 .(41, 42) The Mini-Mental State Exam is a short standardized mental status examination that has been widely employed for clinical and research purposes for global assessment of cognitive functioning.(41) Clients who meet diagnostic criteria for severe depression, cognitive impairment, mania, hypomania, a psychotic disorder, or substance abuse or dependence will require clinical treatment. The research coordinator will also provide referrals for psychiatric care and list of community-based resources to the client. Eligible older adults will be scheduled for a clinical assessment.

Comparison condition. This group will receive 8 weekly visits and phone calls by study staff that will consist of social interaction. The staff member will receive training and receive supervision from the PI. The purpose is to provide social interaction that does not focus on peer support for depression, goal-setting nor self-care skills. Study

staff will monitor for worsening depressive symptoms and the client will be referred to mental health services as appropriate. The telephone visits will be audio-recorded and feedback given during weekly team meetings where study processes and problems will be discussed.

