Qualitative analytic strategy. The audio recordings of semi-structured interviews conducted with multiple stakeholders will be transcribed professionally. The transcripts will be analyzed using thematic analysis which is a flexible and commonly used approach in qualitative analysis. The study team members will proceed through 4 phases: 1) immersion in the data by reading and re-reading the data, 2) generation of initial codes, 3) sorting of codes into themes, and 4) review and refinement of themes based on coded extracts and relevance to the entire dataset. To ensure trustworthiness, the PI and two trained study team members will code a subset of transcripts independently, compare their agreement on segments of coded data and resolve disagreements through in-depth discussion. We will use 80% agreement as a benchmark for acceptable inter-rater reliability. Because we anticipate 10-15 different codes, we do not think it necessary to use a Kappa statistic to correct for chance agreement. The coding scheme will be revised to reflect their feedback prior to coding of the remainder of the transcripts. The PI and study team members will meet on a weekly basis during the data analysis period to discuss in depth the rationale for coding and theme generation, and will resolve disagreements by negotiated agreement. Our advisory board will review and provide feedback on the coding scheme and study results. Qualitative data analytic software, NVIVO11, (QSR Intl, Durham UK) will be used.

- b. Study duration and number of study visits required of research participants.

The study will be 18 months in duration. Research participants in the intervention will have a baseline, 8 meetings with the peer mentor, a post-study assessment and assessments at 3, 6, 9 and 12 months, for a total of 14 study visits. Participants in the control condition will have the same number of study visits.

- c. Blinding, including justification for blinding or not blinding the trial, if applicable.

The person conducting the post-study assessment will be blinded. No other blinding is possible given the nature of the intervention.

- d. Justification of why participants will not receive routine care or will have current therapy stopped.

Patient will be free to obtain depression care outside of the study, as desired.

- e. Justification for inclusion of a placebo or non-treatment group.

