Our primary study aim is to test the effects of the Peer Enhanced Depression Care Program for reducing depressive symptoms compared to Enhanced Usual Care. H1: Older adults randomized to the Peer Program (vs. control) will report decreased depression (PHQ-9 score decrease ≥ 5) at 8 weeks, 3, 6, 9 and 12 months. To assess the immediate effects of treatment, we will fit a mixed effects model(59) with nested random effects for counselor and participant such that $E[y_{ij}] = \beta_0 + \beta_1 tx + \beta_2 week + \beta_3 tx * week$, adjusted for sex and other covariates (see 7.a.), where y_{ij} is the PHQ9 score for the i th individual at intervention week j , β_2 is the rate of change in PHQ-9 for individuals randomized to EUC, and β_3 , the coefficient of interest, is the difference in rates of change in PHQ-9 between the Peer Program and Enhanced Usual Care study arms. To assess durability of the intervention effects, we will model PHQ-9 at each post-intervention follow-up (months 3,6,9 and 12) using a time-averaged model, which adjusts for PHQ-9 at week 8 and models PHQ-9 scores at later time points as a function of treatment assignment.

Sample size and power

We calculated power to detect a difference in rate of PHQ-9 decline over the 8-week intervention period via simulation. Assuming 20% attrition, design effect of 1.2 (to account for clustering within peers (62) based on ICCs from pilot data), and regression parameters from our preliminary data (SD of random intercept: 2.83; SD of random errors: 0.11), with N=160, we would have 99% power to detect a difference in slope of 0.625, which corresponds to a between-group difference of 5 points on the PHQ-9 at 8 weeks. Similarly, we calculated power to detect a sustained post-intervention between-group difference. We will have 99% power to detect a sustained 5-point difference in PHQ-9 during that period.

Data and safety monitoring plan

We will have a Data and Safety Monitoring Board (DSMB) to monitor the study with an attendant monitoring plan that will involve interim analysis. We will provide descriptive data for the first 6 months after the first participant has enrolled in the study to review both the non-serious and serious adverse event rates. We will meet every 6 months and also meet on an ad hoc basis if the real time serious adverse events warrant meeting, in their judgment.

d. Early stopping rules.

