Although we are not studying experimental drugs, the intervention is experimental with the attendant risks. To address this, we will have a Data and Safety Monitoring Board (DSMB) to monitor the study with an attendant monitoring plan. The role of the DSMB will be to ensure that no unexpected, untoward consequences of the experimental intervention occur, and if they do, to implement safeguards to decrease or eliminate future risks. Although the risk is low, the Peer Program could induce emotional distress associated with discussion of past trauma or current stressors. We will include as serious adverse events acts of suicide or attempted suicide and threats of violence or violence toward the research team, providers or outside personal contacts. Any adverse events related to behavior will be provided to the DSMB in real time. These adverse events include, but are not limited to, suicidality, homicidality, or inappropriate or threatening behavior with the research or clinical staff. Less serious adverse events related to the treatment of depression will be compiled and summarized for the DSMB at their scheduled meetings. All other severe adverse events in participants will be monitored by the Principal Investigator, the Study Coordinator, and the Social Workers and will be reported to the DSMB regardless of a priori expectation or investigator assessment of likelihood of the study being the cause of the adverse event.

The DSMB will also have the power to request further data (e.g. depression outcome data) from the Principal Investigator based on any concerns that may be raised in the ongoing investigation in the scientific community. Interim analyses will be performed and compiled for review by the DSMB. At any time during the study, based on its findings, the DSMB can put the study on either temporary hold or stop the study entirely after notifying the Principal Investigator and the IRB. In the rare case in which they have to do so, the DSMB will generate a formal report to the Principal Investigator, the sponsor (NIMH), and the IRB. This report would then be modified for a lay reader, a

version for past participants and current participants would be produced, and the letter would be sent to all past and current study participants and their referring providers.

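### Section 4.c blinds only the post-study assessor and calls any other blinding impossible, leaving the month 3, 6, 9 and 12 PHQ-9 interviews with no blinding provision

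*Combined protocol and SAP*

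**What the plan says.** Section 4.c (Blinding) reads: "The person conducting the post-study assessment will be blinded. No other blinding is possible given the nature of the intervention".

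Section 4.b, immediately before it, lists "a post-study assessment and assessments at 3, 6, 9 and 12 months, for a total of 14 study visits".

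The study flow in section 4.a has participants in both arms "contacted by Study coordinator to conduct interviews by telephone, post-intervention after 8 visits and at 3 months, 6 months, 9 months and 12 months".

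H1 (sections 2 and 6.c) is that participants given the peer programme, compared with control, "will report decreased depression (PHQ-9 score decrease ≥ 5) at 8 weeks, 3, 6, 9 and 12 months". For the later time points, section 6.c states: "To assess durability of the intervention effects, we will model PHQ-9 at each post-intervention follow-up (months 3,6,9 and 12) using a time-averaged model". That model adjusts for the week-8 PHQ-9.

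Two other places bear on who might learn the allocation:
- Section 7.c: "All other severe adverse events in participants will be monitored by the Principal Investigator, the Study Coordinator, and the Social Workers".
- Section 4.a, Comparison condition: the control calls are recorded, with "feedback given during weekly team meetings where study processes and problems will be discussed".

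**The concern.** The plan thought assessor blinding worth having at week 8, then ruled it out elsewhere on a ground that does not apply to assessors. The nature of the intervention explains why participants, peer mentors and the staff making control calls cannot be blinded. It does not explain why a telephone interviewer at month 6 cannot be.

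Followed as written, 4.c leaves the whole durability outcome without assessor blinding. Any interviewer effect that differs by arm at months 3 to 12 is systematic, so averaging the four follow-ups does not dilute it. If it arises only after week 8, adjustment for the week-8 score does not remove it either. Apparent persistence or fading of the effect could then partly reflect how the later scores were collected.

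**Working it through.** **1. Does the post-study assessment mean one visit or every later visit?**

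The plan's own figure is 14 study visits (4.b).
- Post-study assessment counted as one visit: 1 baseline + 8 meetings + 1 post-study + 4 follow-ups = 14. This reproduces the plan.
- Post-study used as a label for the follow-ups, with no separate visit: 1 + 8 + 4 = 13. This does not.

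The payment schedule in section 9.a agrees. It lists baseline, week 8 and months 3, 6, 9 and 12 separately: 6 × $30 = $180.

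**2. What does 4.c cover?**

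| Interview | Conducted by (4.a) | Analysis using it (6.c) | Blinding provided (4.c) |
|---|---|---|---|
| Week 8 | Study coordinator, telephone | Slope model; adjustment term in durability model | Yes |
| Months 3, 6, 9, 12 | Study coordinator, telephone | Durability outcome | None |

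Blinding is provided for 1 of 5 post-baseline interviews, and for 0 of the 4 durability outcomes.

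**3. Is other blinding impossible?**

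The same role, by the same means and in both arms, does all five interviews. If it can be blind just after the intervention ends, nothing in the intervention prevents blinding one or more months later. Sections 4.a and 4.c conflict on this point.

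**4. Could the assessor learn the arm?**

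The Study Coordinator shares adverse-event monitoring with the social workers, and social workers supervise the peers. Recordings of control calls lead to feedback at team meetings. Either route could reveal allocation. Both operate during weeks 1 to 8, so they bear on the week-8 interview as well.

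**5. How much could it matter? (illustration only)**

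Inputs from section 6.c: N = 160 randomised 1:1, 20% attrition, design effect 1.2, random-intercept SD 2.83, two-sided α = 0.05. Assumptions not in the documents: interviewer bias b of 0.5 or 1.0 PHQ-9 point, an alternative SD of 5, and no true effect.

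- Effective n per arm = 80 × 0.8 / 1.2 = 53.3
- SE = SD × √(2 / 53.3): 0.55 for SD 2.83, and 0.97 for SD 5
- Rejection probability = P(Z > 1.96 − b/SE) + P(Z < −1.96 − b/SE)

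| Assumed bias | SD 2.83 | SD 5 |
|---|---|---|
| 0.5 | 14.9% | 8.1% |
| 1.0 | 44.6% | 17.8% |

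The assumed bias is 0.5/5 = 10% to 1.0/5 = 20% of the 5-point difference the trial is powered for. A constant shift is unchanged by pooling: (b + b + b + b)/4 = b. The calculation is a test at one time point. It leaves out the week-8 adjustment and the averaging over months 3 to 12.

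**The case against.** **Unblinded follow-up is not stated.** A reader might infer that four of the five H1 time points will be read out by an interviewer who knows the arm. The documents do not say so. Section 4.c blinds a person, and if that person makes every call, they might still be blind at month 12. Equally, 4.a names a role, not an individual. This objection stands: what can be said is that the plan makes no provision for blinding and calls it impossible.

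**The routes to unblinding are possible, not certain.** The Comparison condition text does not say the coordinator attends the team meetings, and 7.c says only that events are monitored. Because both routes operate before week 8, a clean contrast between a protected week 8 and exposed later calls is also unsupported. This stands.

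**The early result is not well protected either.** The week 0–8 analysis is a slope fitted to weekly PHQ-9 scores. Section 7.b has peers collect these in the intervention arm. Of the eight post-baseline scores scheduled in Table 3 (weeks 1 to 8), at most one comes from the blinded assessor. Extending assessor blinding does not protect the other weekly scores.

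**PHQ-9 is self-report, and participants are told their assignment.** Expectation effects remain whatever the assessor knows. This limits the benefit of the fix but does not cancel it: the items are put to participants by an interviewer, and the plan itself chose to blind that interviewer at week 8.

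**The coordinator may not be the only assessor.** Table 3 also schedules a clinician-assessed MINI at week 8 and at each follow-up. A clinical social worker does it at baseline, and social workers supervise the peers. The MINI is not a named outcome, but wording confined to the coordinator would leave it open.

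None of this rescues the impossibility statement, which is broader than its reason and conflicts with the study flow.

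**Conclusion.** The concern holds as a gap in provision together with an incorrect statement of impossibility. Assessor blinding is provided for one of five post-baseline interviews and for none of the four in the durability analysis, although the plan's own staffing shows that it could be.

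The 8% to 45% range should not be read as the type I error of the planned test. It reproduces on its inputs, but the bias sizes and the SD of 5 are assumed, 2.83 is a random-intercept SD, and the planned model is a time-averaged one adjusted for week 8. It shows only that a bias small relative to the 5-point target could matter.

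No sample size, power or alpha figure changes. This should be fixed, and before follow-up interviews begin, because blinding once lost cannot be restored.

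**What to change.** 1. In 4.c, state that whoever conducts the 8-week and the 3-, 6-, 9- and 12-month telephone outcome assessments will be blinded to arm, and that participants will be asked at the start of each call not to mention their programme. Say whether this covers the follow-up MINI.
2. Confine the statement that no other blinding is possible to participants, peer mentors and the staff delivering the intervention or control calls.
3. Keep the outcome assessor out of team discussion of session recordings and out of adverse-event review that identifies the arm. Reconcile this with three places: the urgent-referral flag in the 4.a study flow, the reporting of self-harm to a Program Coordinator in 7.b (whose relation to the Study Coordinator is undefined), and the monitoring duties in 7.c. The assessor must still be able to flag urgent concerns.
4. Acknowledge that the weekly PHQ-9 scores in the week 0–8 slope are outside this protection, because peers collect them in the intervention arm.

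**Cost:** protocol wording and a small reallocation of duties among existing staff. The Principal Investigator and social workers already share adverse-event monitoring. Blinded post-baseline interviews provided for would rise from 1 to 5. If the follow-up MINI is to be blinded too, its assessor has to be named, and the documents do not show whether existing staff could cover that.

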Clinical staff at Beacham clinic at Bayview will refer patients using EPIC in basket. Study staff will obtain the patient contact information, (name, address and telephone number) from Epic and send a letter describing the study to the patient to opt in to the study. The letter will contain a number to call and a card to mail if they want to receive any communications from the study. If they want more details, we will provide it. We will ask if they would like to undergo a phone screening. If they agree, study staff will do a phone screen. The patient's name, address and telephone number will be entered into a database that will be stored in a secure Massachusetts General Hospital server. Any PHI of participants who do not contact us will be destroyed within 6 months. PHI of patients who call us will be saved per protocol. We add another method of referral because we have not gotten enough referrals with flyers and PCPs say they would like to refer but their busy clinic schedule is a significant barrier. PCPs say that ability to refer through EPIC will facilitate referrals..

Clinical assessment. A clinical social worker will perform the clinical assessment by telephone. She will repeat the PHQ-9 and conduct an assessment for Major Depression, manic episodes, alcohol abuse, substance abuse and psychotic disorders using the MINI (Mini-International Neuropsychiatric Interview). The clinical assessment will ensure that the participants are appropriate for a peer program in terms of depression severity and acute psychiatric symptoms. The clinical assessment will include history of present illness, psychiatric and medical history as well as psychosocial assessment for use by the social worker to provide relevant guidance to peer mentors during weekly supervision meetings. If the older adult is eligible after the clinical assessment, oral consent for participation in the study will be obtained and oral consent form will be mailed to the participant. After oral consent is obtained, the participants will undergo a baseline assessment. The assessment will consist of questions to obtain demographic information, medical use and depression care history as well as questionnaires to measure primary and secondary outcomes and mediators. Then the participants will be randomized to intervention or Social Interaction Control. The clinical and baseline data will be stored in a secure online Massachusetts General Hospital server that only study staff will be able to access.

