Secondary outcomes will be engagement, coping, health service use, emotional, social and physical function. Engagement will be defined in two ways: 1) as attendance of 80% of meetings as reported by peer mentors (45) and 2) score on the Working Alliance Inventory-SR, a short 7-item questionnaire that measures affective bond, agreement on tasks and goals, and has been used to measure working alliance in non-professional relationships in mental health.(46, 47) Studies of working alliance typology has shown the sensitivity of this instrument in repeated assessments.(48) Service use will be measured with the Cornell Service Index, a questionnaire that includes use of both clinical and informal community-based health services and used in depression care studies among older adults.(49) Physical, social and emotional functioning will be assessed using the Medical Outcomes Short Form (SF-36).(50, 51) Self-efficacy will be measured with the General Self Efficacy Scale, a 10-item scale validated for use in multicultural populations. (52) Loneliness will be measured with the R-UCLA loneliness scale, a commonly used, 20-item, self-report questionnaire.(53) The Brief Coping is widely used in depression studies which assesses trait and state coping developed from the COPE inventory which assesses different coping dimensions.(54)

Covariates. We will obtain sociodemographic factors by self-report that will include age, education level, marital status, ethnicity, medical comorbidity, past and current depression treatment. We will use the Life Events Questionnaire to measure changes occurring in the past year and the impact of the event on a 4-point scale.(55, 56) Medical comorbidity will be measured with the WHO WMH CIDI that has been established for use among older adults and has proven validity and reliability.(57) New uptake of depression care services such as professional counseling and antidepressant medications will be obtained by self-report at each meeting by the peer mentor to assess for service use during the intervention. These variables will be used to describe the sample, compare intervention and control groups and used as covariates in analyses. Health-related social determinants consisting of 5 core components such as housing, food, transportation, utility needs, and safety will be measured with the Accountable Health Communities Core Health-Related Social Needs Screening Questions. (58)

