Primary analyses will be intention-to-treat. Descriptive statistics (e.g. frequencies, means, standard deviations, medians, interquartile ranges) and graphic displays will be generated for all study variables to ensure that distributional and other assumptions of the planned analyses are met. We will minimize missing data using our team's documented retention strategies that have resulted in only 14% attrition.³⁷ All primary analyses will be adjusted for sex, demographic factors, life events, medical comorbidity, and use of mental health services. Hypothesis tests will be two-sided with $\alpha=0.05$.

c. Statistical plan including sample size justification and interim data analysis.

Table 3. Assessment schedule														
Variable	Measure	Timing of assessments												
		0 wk	1 wk	2 wk	3 wk	4 wk	5 wk	6 wk	7 wk	8 wk	3 mth	6 mth	9 mth	12 mth
Sociodemographic factors	Self-report	x												
Depression (self-report)	PHQ-9	x	x	x	x	x	x	x	x	x	x	x	x	x
Depression (assessed by clinician)	Mini-International Neuropsychiatric Interview (MINI)	x								x	x	x	x	x
Client engagement	At least 80% attendance of meetings, peer logs of meetings	x	x	x	x	x	x	x	x	x				
Client engagement	Working Alliance Inventory-SR	x	x	x	x	x	x	x	x	x				
Physical, social and emotional function	Medical Outcomes Study Short Form 36	x								x	x	x	x	x
Self-efficacy	General Self Efficacy Scale	x	x	x	x	x	x	x	x	x		x		x
Loneliness	R-UCLA Loneliness Scale	x	x	x	x	x	x	x	x	x		x		x
Coping skills	Brief Copie	x								x	x	x	x	x
Medical comorbidity	WHO WMH CIDI	x								x	x	x	x	x
Clinical and community health service use	Cornell Service Index	x								x	x	x	x	x
New uptake of counseling and antidepressant	Self-report	x	x	x	x	x	x	x	x	x				
Social determinants of Health	Accountable Health Communities Core Health-Related Social Needs Screening Questions	x								x	x	x	x	x

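### Primary intention-to-treat models adjust for undated use of mental health services, which lets in uptake measured after randomisation; the covariates should be restricted to pre-randomisation values

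*Combined protocol and SAP*

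**What the plan says.** The last paragraph of section 6.b states: "Primary analyses will be intention-to-treat". It continues: "All primary analyses will be adjusted for sex, demographic factors, life events, medical comorbidity, and use of mental health services". Neither sentence says when service use is measured.

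The Covariates paragraph of 6.b names two kinds of service variable. One can be read as a baseline item: "past and current depression treatment". The other is new uptake of professional counselling and antidepressants, "obtained by self-report at each meeting by the peer mentor to assess for service use during the intervention". The paragraph then says that these variables will be "used to describe the sample, compare intervention and control groups and used as covariates in analyses", without saying which analyses.

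Three other places bear on timing:
- Section 4.a (Clinical assessment) takes "demographic information, medical use and depression care history" before randomisation.
- Section 6.b makes health service use a secondary outcome: "Service use will be measured with the Cornell Service Index".
- Table 3 schedules the row "New uptake of counseling and antidepressant" weekly from week 0 to week 8, and the Cornell index at weeks 0 and 8 and months 3, 6, 9 and 12.

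The 8-week model in 6.c adjusts for sex and other covariates and refers the reader to 7.a, which is the Medical risks section.

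**The concern.** An intention-to-treat contrast compares the arms as randomised, including whatever the programme does to later care. Adjusting for a variable that treatment or the evolving outcome can change replaces that contrast with a different one. Service use after randomisation is such a variable here, for three reasons:
- **The programme acts on it.** Section 2 lists linking participants to clinical and community services as a core component. Section 4.a makes this part of the peer's role and has referral offered during peer meetings.
- **The outcome acts on it.** Sections 4.a and 4.f have participants referred when depression worsens, in either arm.
- **It is itself an outcome.** Service use is a planned secondary endpoint.

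Two analysts could both follow the text and estimate different quantities, and the choice could be made after the data are seen.

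**Working it through.** **1. The plan's own figure.** The inputs, from 6.c, are N = 160, 20% attrition, design effect 1.2, error SD 0.11 and a slope difference of 0.625 per week.
- 0.625 × 8 = 5.0 points, as stated.
- Effective n per arm = 160 × 0.8 / 1.2 / 2 = 53.3.
- For weeks 0 to 8, the sum of (week − 4)² is 60, so the SE of the slope difference = (0.11/√60) × √(2/53.3) = 0.00275.
- Power is about 100%, in line with the stated 99%.

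No covariate enters these inputs, so dating the covariates changes neither N nor stated power. It changes only what is estimated.

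**2. The texts side by side.**

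| Place | Service variable | Timing |
|---|---|---|
| 6.b, primary analyses | use of mental health services | not stated |
| 6.b, Covariates | past and current depression treatment | can be baseline |
| 6.b, Covariates | new uptake | during the intervention |
| Table 3 | new uptake | weeks 0 to 8 |
| Table 3 | Cornell Service Index | week 0 and five later times |
| 6.c, 8-week model | cross-reference to 7.a | does not resolve it |

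Nothing limits the covariate to baseline.

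**3. What an uptake term does to the 8-week coefficient.** The coefficient of interest is β₃ (treatment × week). Effects are given below as absolute 8 × β₃. Let p_T and p_C be the proportions who have taken up services by week 8 in the peer and control arms, rising linearly from zero, and let g be the number of points by which services lower PHQ-9. The documents give none of these, so they are assumptions. Services then contribute g × (p_T − p_C) to the 8-week difference. With a direct effect of 5.0, p_C = 8%, p_T = 28% and g = 2:
- no service term: 5.0 + 2 × 0.20 = 5.4;
- uptake effect fully adjusted out: 5.0;
- gap: 0.4 points, or 0.4/5 = 8% of the design difference.

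**4. The form of entry decides whether this happens.** Large simulations of this scenario used a random-intercept model, the protocol's intercept SD of 2.83 and an assumed residual SD of 2. One run with n = 200,000 gave:

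| Service term in the model | 8 × β₃ |
|---|---|
| none | 5.39 |
| time-constant main effect | 5.39 |
| time-constant plus uptake-by-week | 5.00 |
| time-varying | 5.00 |

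An independent repeat gave 5.36 with no term or a time-constant term, and 4.98 with either of the other two. A time-constant main effect does not touch β₃. A time-varying term or an uptake-by-week term does. In a run with equal uptake (8% in each arm), all forms compared gave 4.99.

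**5. Range of the gap, g × (p_T − p_C).**

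| Uptake difference (peer minus control) | g = 2 | g = 4 |
|---|---|---|
| 0 | 0 | 0 |
| 10 percentage points | 0.2 | 0.4 |
| 20 percentage points | 0.4 | 0.8 |
| 30 percentage points | 0.6 | 1.2 |

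**6. Direction.** If severity drives uptake, the control arm may use more services. With 18% control, 13% peer and g = 2, the formula gives 5.0 + 2 × (0.13 − 0.18) = 4.9 without the term. The simulation gave 4.88 without it and 4.99 with a time-varying term, so adjustment enlarges the estimate.

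**7. Months 3 to 12.** This model has no treatment-by-week term, so a service covariate acts on the treatment coefficient directly. With an assumed direct effect of 2, the coefficient went from 2.41 to 2.01 in one scenario (uptake 20% control and 40% peer, g = 2) and from 2.01 to 2.34 in another (20% and 50%, uptake linked to later severity, g = 0).

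**The case against.** The strongest reply is that this is loose wording rather than a demonstrated error. A baseline reading is available, since depression care history is taken before randomisation. For the durability model, 6.c names only week-8 PHQ-9 and treatment. The 8-week route is also narrow: it needs a post-baseline reading, a particular form of entry, unequal uptake and a service effect. Section 4.a places resource linkage at the end of the programme, with the resource list given at the eighth meeting, and 4.f notes that appointments are hard to get quickly. Referral for worsening applies to both arms.

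All of that stands, and it limits the claim. It does not remove the ambiguity, because the Covariates paragraph expressly includes uptake during the intervention, and referral is offered during peer meetings before week 8.

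Three stronger readings are tempting, and the documents do not support them:
- **That the primary result will be biased, or biased against the programme.** The documents state no uptake rates, no arm difference and no service effect, and adjustment can move the estimate either way.
- **That any post-randomisation service covariate distorts the 8-week slope.** A time-constant main effect leaves it unchanged.
- **That the month 3 to 12 shifts measure departure from the total effect of randomisation.** Both versions already condition on week-8 PHQ-9, so neither is that effect.

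**Conclusion.** The concern holds as a specification gap that should be closed before analysis. The plan promises intention-to-treat, yet it permits, and taken literally includes, a covariate measured after randomisation that the programme and the outcome can both change. If it enters and uptake differs by arm, the reported coefficient is not the promised effect.

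The size is unknown. The 8-week illustration of about 5.4 to 5.0 points rests on assumed uptake (8% and 28%), an assumed 2-point service effect, and entry as a time-varying or uptake-by-week term. The shift is zero with a time-constant main effect, and also in the equal-uptake case shown. For months 3 to 12, only the possibility of a shift in either direction can be stated. Confidence is high about the wording gap, but this does not extend to any particular bias.

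**What to change.** In sections 6.b and 6.c:
- State that demographic factors, life events, medical comorbidity and use of mental health services enter the primary models only as values measured before randomisation. Comorbidity needs this too, because Table 3 repeats it after baseline.
- Define service use as the pre-randomisation self-report of past and current depression treatment. The Cornell index also covers informal community services, so it is not the same variable.
- Edit the Covariates paragraph so that new uptake and post-baseline service use are not covariates in the primary models. Then point the cross-reference to 7.a at that edited list. Redirecting it without the edit would bring new uptake back in.
- Keep post-baseline service use for description, or as the planned secondary outcome with the Cornell index. Compare new uptake between arms only if it is collected in the same way in the control arm. The text describes collection by peer mentors, whom controls do not have, and Table 3 does not separate the arms.
- State that life events are taken at baseline, since Table 3 has no row for them.

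The week-8 PHQ-9 term in the durability model is a separate issue and is not changed by this rule.

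The cost is a few sentences and one stated baseline timing for life events. Depression care history and comorbidity are already collected before randomisation, and N and the stated power are unaffected.
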